1.3 RATIONALE FOR PERFORMING THE TRIAL

BI 730357 is being developed for the treatment of patients with moderate-to-severe PsO, and other disease indications (e.g., psoriatic arthritis (PsA) axSpA, CD, and NASH) where there remains an unmet medical need.

Preclinical data indicate that BI 730357 has phototoxicity potential.

The current trial is being performed to assess the photosafety of BI 730357 compared to placebo and the known photosensitizing agent ciprofloxacin in healthy volunteers.

Safety data provided by this trial will support further clinical development program of BI 730357 in patients with diverse indications.

1.4 BENEFIT - RISK ASSESSMENT

1.4.1 Benefits

Participation in this trial is without any (therapeutic) benefit for healthy subjects. Their participation in the trial, however, is of major importance to the development of BI 730357 and may help to generate future benefit for larger groups of patients with many disease indications.

1.4.2 Risks

The subjects are exposed to the risks related to the exposure to the trial medication and the risks of the trial procedures.

Drug-related risks and safety measures

BI 730357

The pharmacological effects of BI 730357 are dose dependent, and no evidence for prolonged or irreversible effects has been observed.

As described in Section 1.2, the non-clinical BI 730357 safety data together with the safety data from trials in healthy volunteers (HV) and patients with plaque PsO demonstrated an acceptable profile to support clinical trials in males and females, including WoCBP.

Since preclinical data indicate that BI 730357 has phototoxicity potential, subjects in this trial will be kept in the clinic on all dosing days up until completion of photosensitivity assessments 72 hours after last dose and not allowed to expose themselves to the direct sunlight. Additionally, subjects will be advised to apply protection measures up to the end of trial visit, as described in section 4.2.2.2.

c27983101-03 Clinical Trial Protocol Page 22 of 79

Proprietary confidential information © 2020 Boehringer Ingelheim International GmbH or one or more of its affiliated companies

Preclinical data indicate that BI 730357 has DDI potential. During the trial, drugs or foods which are known strong or moderate inhibitors or inducers of CYP3A4, or drugs which are sensitive substrates of CYP1A2 or CYP2B6 will be prohibited. Additionally, substrates of

P-gp are also to be excluded during the trial BI 730357 is confirmed as a sensitive cytochrome P450 (CYP) 3A substrate, based on clinical drug-drug interaction (DDI) evaluation with itraconazole, a CYP3A inhibitor, in trial 1407-0014. Drugs or foods that are known CYP3A inhibitors or strong or moderate CYP3A inducers should not be co-administered in clinical trials with BI 730357. Based on *in vitro* data, BI 730357 could potentially induce CYPs 1A2, 2B6, 2C8, 2C9, or 2C19 in human. Substrates of CYPs 1A2, 2B6, 2C8, 2C9, or 2C19 for which a reduction in exposure could present a potential patient risk should not be given together with BI 730357. Additionally, based on *in vitro* data, BI 730357 may inhibit a number of transporters in human; based on the magnitudes of the *in vitro* inhibition, it is recommended that sensitive substrates of P-gp, BCRP, OATP1B1, OATP1B3, OAT3, OCT2, MATE1, and MATE2-K that have narrow therapeutic windows should be avoided (refer to Appendix 10.1).

As with other immune-targeted therapies, impaired host defence is a theoretical target-related toxicity, potentially resulting in increased risk of infection and/or malignancy. Subjects with latent TB infection or TB disease, also subjects with HBV, HCV, HIV or any other clinically relevant bacterial or fungal infections will be excluded at screening.

Risk to subjects will also be minimized in this trial by implementing conservative eligibility criteria.

Homozygous, but not heterozygous RORC knockout mice have a high incidence of T cell lymphoma, thought to originate in the Thymus. While the translatability of the knockout phenotype to pharmacological RORγ antagonism and to humans is unknown, this raises the hypothetical concern for clinical T cell lymphoma risk. The exact cause of T cell lymphomas in RORC knockout mice is not fully understood, but changes in homeostasis in the thymus, such as thymocyte apoptosis and proliferation, are thought to play a role. AEs and SAEs consistent with malignancy, and specifically those representing lymphoma, will be carefully monitored and evaluated as well as monitoring of peripheral blood lymphocyte subsets will be integrated into this clinical trial.

An *in vivo* phototoxicity study in rats was conducted in pigmented rats. No cutaneous reactions indicative of phototoxic response were seen at 10 mg/kg/day, which corresponded to mean C_{max} and AUC_{0-24} values of 4,520 nM and 35,200 nM•h, respectively. No ophthalmic changes indicative of phototoxicity were seen up to 30 mg/kg/day, which corresponded to a mean C_{max} and AUC_{0-24} values of 13,500 nM and 107,000 nM•h, respectively.

Dose 400 mg BI 730357 planned to be tested in this study was administered once daily over a period of 4 weeks in the MRD study 1407-0002. The pharmacokinetic parameters observed in this study - AUC_{0-24} [nmol*h/L] 15,600 ($AUC_{\tau,ss}$ [nmol*h/L] 35,500) and C_{max} [nmol/L] 1320 ($C_{max,ss}$ [nmol/L] 2210) indicate that the plasma concentrations and exposures, which might be achieved in this study, are lower than those observed in *in vivo* phototoxicity study in rat where the phototoxic responses have been seen.

c27983101-03 Clinical Trial Protocol Page 23 of 79

Proprietary confidential information © 2020 Boehringer Ingelheim International GmbH or one or more of its affiliated companies

Ciprofloxacin

The most frequently reported adverse reactions, from clinical trials of all formulations, all dosages, all drug therapy durations, and for all indications of ciprofloxacin therapy were nausea (2.5%), diarrhoea (1.6%), liver function tests abnormal (1.3%), vomiting (1%), and rash (1%).

Changes in laboratory parameters while on CIPRO are listed below:

Hepatic -Elevations of ALT (SGPT), AST (SGOT), alkaline phosphatase, LDH, serum bilirubin.

Hematologic-Eosinophilia, leukopenia, decreased blood platelets, elevated blood platelets, pancytopenia.

Renal-Elevations of serum creatinine, BUN, crystalluria, cylindruria, and hematuria have been reported.

Other changes occurring were: elevation of serum gammaglutamyl transferase, elevation of serum amylase, reduction in blood glucose, elevated uric acid, decrease in hemoglobin, anemia, bleeding diathesis, increase in blood monocytes, and leucocytosis.

Fluoroquinolones, including CIPRO, have been associated with disabling and potentially irreversible serious adverse reactions from different body systems that can occur together in the same patient. These adverse reactions include:

- Tendinitis and Tendon Rupture
- Peripheral Neuropathy
- Central Nervous System Effects
- Exacerbation of Myasthenia Gravis
- Other Serious and Sometimes Fatal Adverse Reactions
- Hypersensitivity Reactions
- Hepatotoxicity
- Serious Adverse Reactions with Concomitant Theophylline
- Clostridium difficile Associated Diarrhea
- Prolongation of the QT Interval
- Musculoskeletal Disorders in Pediatric Patients
- Photosensitivity/Phototoxicity
- Development of Drug Resistant Bacteria

These reactions can occur within hours to weeks after starting CIPRO. Patients of any age or without pre-existing risk factors have experienced these adverse reactions. These events may be severe and generally occur following the administration of multiple doses.

c27983101-03 Clinical Trial Protocol Page 24 of 79

Proprietary confidential information © 2020 Boehringer Ingelheim International GmbH or one or more of its affiliated companies

As with all drugs, the potential for hypersensitivity and allergic reactions has to be taken into consideration.

Although rare, a potential for drug-induced liver injury (DILI) is under constant surveillance by Sponsors and regulators. Therefore, this trial requires timely detection, evaluation, and follow-up of laboratory alterations in selected liver laboratory parameters to ensure patients' safety (see also section 5.2.6.1.4).

Special precautions

The following safety measures will be applied in order to minimize the risk for healthy volunteers:

- Dose selection is based on a sound preclinical package, and safety, tolerability and PK data from MRD administration of BI 730357 up to 400 mg in healthy volunteers and preliminary safety data for up to 200 mg in patients with plaque psoriasis.
- Dose duration of 500 mg of ciprofloxacin bid over 5.5 days is a standard, well tolerated clinical dose
- Individual stopping rules as described in section 3.3.4.1 will be applied.
- UV-light protection measures as described in section 4.2.2.2 will be required until the end of study visit.
- The subjects will be kept in a Phase I unit during trial medication administration until completion of photosensitivity assessments 72 hours after last dose for safety evaluations. A careful clinical examinations will be performed during the trial, before the subjects are discharged from the clinic, and at the end of trial visit.
- Adverse events, body temperature, vital signs, ECGs and safety laboratories will be monitored at different time points during the trial. During the safety follow-up period all AEs, regardless of relatedness, will be collected up to 7 days after the last administration of trial medication.

Procedure-related risks

Blood sampling by venepuncture or through an indwelling venous catheter may be accompanied by mild bruising and also, in rare cases, by transient inflammation of the wall of the vein. In addition, in rare cases a nerve might be injured while inserting the venous catheter, potentially resulting in paraesthesia, reduced sensibility, and/or pain for an indefinite period.

The total volume of blood withdrawn per subject during this trial will not exceed the volume of a normal blood donation (500 mL). No health-related risk is expected from this blood withdrawal.

Boehringer Ingelheim

BI Trial No.: 1407-0037

Clinical Trial Protocol c27983101-03

Page 25 of 79 Proprietary confidential information © 2020 Boehringer Ingelheim International GmbH or one or more of its affiliated companies

01 Apr 2020

Based on the findings in the nonclinical studies conducted to date and in accordance with international regulatory guidelines, the inclusion of women of childbearing potential (WoCBP) in this study is justified. To minimize the risk of unintentional exposure of an embryo or foetus to the investigational drug, WoCBP must agree to the requirements for pregnancy testing and contraceptive methods described in this protocol. There are no specific contraceptive requirements for male participants.

Potential risks of clinical relevance for this trial	Summary of data, rationale for the risk	Mitigation strategy	
Investigational Medicinal Products:			
Drug-induced liver injury (DILI)	Rare but severe event, thus under constant surveillance by Sponsors and regulators.	 Timely detection, evaluation, and follow-up of laboratory alterations in selected liver laboratory parameters to ensure patients' safety. Drug interruption or discontinuation if applicable. 	
Infection and/or malignancy	Impaired host defence typical for immune-targeted therapies	 Subjects with latent TB infection or TB disease at screening will be excluded. Patients with HBV, HCV or HIV infection will be excluded. AEs and serious adverse events (SAEs) consistent with malignancy or infections are to be evaluated. 	
Phototoxicity potential	 Long persistence of BI 730357 in dermal tissues. Known phototoxicity potential of Ciprofloxacin 	• Apply protection measures such as sunscreen and sunglasses during therapy and up to 7 days after last drug exposure. Prohibition of treatment with ultraviolet light or medications with known phototoxicity potential up to 7 days after last drug exposure.	

c27983101-03 Clinical Trial Protocol Page 26 of 79

Proprietary confidential information © 2020 Boehringer Ingelheim International GmbH or one or more of its affiliated companies

Potential risks of clinical relevance for this trial	Summary of data, rationale for the risk	Mitigation strategy
Investigational Medicinal Products:		
Hypersensitivity	General precautions	 Subjects with known hypersensitivity to investigational drugs will be excluded at screening. Discontinue investigational drugs immediately at the first appearance of a skin
		rash, jaundice, or any other sign of hypersensitivity and supportive measures instituted.
Prolongation of the QT Interval	Known potential of Ciprofloxacin	Subjects with known prolongation of the QT interval, risk factors for QT prolongation or torsade de pointes will be excluded at screening.
Trial procedures		
• Inflammation of the wall of the vein. Injuring of a nerve while inserting the venous catheter, potentially resulting in paraesthesia, reduced sensibility, and/or pain for an indefinite period.	General risk, acceptable in frame of the study participation	Evaluation of the medical expertise of the trial sites is part of site feasibility assessment

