10. APPENDICES

10.1 RESTRICTED MEDICATION AND FOOD

Other investigational products	• 30 days or 5 half-lives, whatever is longer, prior to randomization through EOT
Disease, surgery	Major surgery performed within 8 weeks prior to screening visit or planned within 8 weeks after screening visit (e.g. hip replacement)
-Drugs or foods (e.g., seville oranges, grapefruit, paw paw and their products) which are strong or moderate inhibitors or inducers of CYP3A4 (e.g, rifampicin, phenytoin), or -Sensitive substrates of CYP1A2 (e.g., alosetron, duloxetine, melatonin, ramelteon, tasimelteon, theophylline, tizanidine, and caffeine when used as a medication), or -Sensitive substrates of CYP 2B6 (e.g., bupropion).	 One week prior to randomisation until EOT (Sensitive substrates of CYP3A4 are not excluded from the trial).
Drugs which are substrates of P-gp (e.g. dabigatran, digoxin and fexofenadine etc.)	One week prior to randomisation until EOT
Drugs with known phototoxic or photoallergic potential (e.g., tetracyclines, fluoroquinolones)	One week prior to randomisation until EOT
BCG (Bacillus Calmette-Guérin) vaccine	1 year prior to randomisation through 1 year after last administration of study drug

c27983101-03 Clinical Trial Protocol Page 75 of 79

Proprietary confidential information © 2020 Boehringer Ingelheim International GmbH or one or more of its affiliated companies

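### Appendix 10.1 and section 4.2.2.2 restrict fewer interacting drugs and foods than section 1.4.2 advises against: a small safety mismatch that touches no endpoint

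*Protocol*

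**What the plan says.** Protocol 1.4.2 makes two statements on interactions, one directly after the other.

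- **First statement.** It begins "During the trial, drugs or foods which are known strong or moderate inhibitors or inducers of CYP3A4" and prohibits these, together with sensitive substrates of CYP1A2 or CYP2B6. P-gp substrates are excluded as well.
- **Second statement.** It reports that "BI 730357 is confirmed as a sensitive cytochrome P450 (CYP) 3A substrate", citing a clinical interaction study with itraconazole, and then says "Drugs or foods that are known CYP3A inhibitors or strong or moderate CYP3A inducers should not be co-administered" in trials of the compound. On substrates of CYP1A2, 2B6, 2C8, 2C9 and 2C19, the sentence ends "2C19 for which a reduction in exposure could present a potential patient risk should not be given together with BI 730357". On transporters, it recommends that "sensitive substrates of P-gp, BCRP, OATP1B1, OATP1B3, OAT3, OCT2, MATE1, and MATE2-K that have narrow therapeutic windows should be avoided" and refers to Appendix 10.1.

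Appendix 10.1 lists drugs or foods "which are strong or moderate inhibitors or inducers of CYP3A4", sensitive substrates of CYP1A2 and CYP2B6, and "Drugs which are substrates of P-gp". The window for these rows is "One week prior to randomisation until EOT".

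Section 4.2.2.1 starts from a general bar on concomitant treatment. It then permits symptomatic AE therapy at the investigator's judgment, names Appendix 10.1 as the place for the interaction list, and refers investigators to the Investigator's Brochure or the sponsor. Section 4.2.2.2 restricts foods only if they are strong or moderate CYP3A inhibitors. The stopping rule in 3.3.4.1 cites section 4.2.2 and Appendix 10.1. Exclusion 7 cites 4.2.2.1 and adds a catch-all for any drug likely to interfere with safe conduct.

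**The concern.** The appendix follows the first statement in 1.4.2 and not the second. An investigator who picks a medicine for an adverse event and checks the list could give one that 1.4.2 says to avoid, and nothing in the list would show it. A reader who follows the cross-reference from the sentence on eight transporters finds one of them.

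Two different things are at stake. A CYP3A inhibitor could raise exposure to BI 730357 itself. The omitted substrate classes concern the safety of the co-administered medicine, whose own levels BI 730357 might change.

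**Working it through.** No statistical figure bears on this point. The check is a comparison of texts, a count, and a look at who is exposed and when.

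**Side by side**

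| Item | 1.4.2, first statement | 1.4.2, second statement | Appendix 10.1 |
|---|---|---|---|
| CYP3A inhibitors | strong or moderate | any known | strong or moderate |
| CYP3A inducers | strong or moderate | strong or moderate | strong or moderate |
| CYP1A2, 2B6 substrates | sensitive | if reduced exposure is a potential risk | sensitive |
| CYP2C8, 2C9, 2C19 substrates | not named | if reduced exposure is a potential risk | not listed |
| P-gp substrates | all | sensitive, narrow window | all |
| BCRP, OATP1B1, OATP1B3, OAT3, OCT2, MATE1, MATE2-K substrates | not named | sensitive, narrow window | not listed |

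Inducers agree throughout, so the CYP3A gap concerns inhibitors weaker than moderate. For P-gp the appendix is wider than the second statement. For CYP1A2 and CYP2B6 it drops the patient-risk condition but keeps a sensitivity limit. I count all three as covered.

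**Count of substrate classes**

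- Named in the second statement: 5 CYPs + 8 transporters = 13.
- In Appendix 10.1: 2 CYPs + 1 transporter = 3.
- Absent: 13 − 3 = 10 (3 CYPs and 7 transporters).

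Some of the absent classes are ones the protocol singles out elsewhere. Section 1.2 reports in vitro data pointing to possible clinically relevant inhibition of MATE1 or MATE2-K, and possible intestinal BCRP inhibition at oral doses above 22 mg. The single doses here are 400 / 22 = 18.2 and 300 / 22 = 13.6 times that figure.

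**Who can be affected** (group sizes from 3.2)

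- BI 730357: 27 + 27 = 54.
- Placebo: 9 + 9 = 18. Ciprofloxacin: 12.
- Total: 54 + 18 + 12 = 84. An interaction with BI 730357 can arise only in the 54.

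**When** (3.1, the flow charts, and the residual effect period in 1.2)

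- Residence runs from Day −1 to Day 11. It covers all dosing days (1 to 8), the Day 8 irradiation, and every on-treatment skin assessment to 72 hours.
- The residual effect period ends on Day 8 + 7 = Day 15, which is also the day of the EOT visit.
- Drug may therefore still be present on Days 12 to 15, four days outside the unit. No dose, irradiation or photosensitivity assessment falls on those days.

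**What the documents do not give:** the exposure increase caused by a CYP3A inhibitor weaker than moderate, and the number of subjects likely to take an omitted medicine.

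**The case against.** The strongest reply is that Appendix 10.1 is not the controlling rule. Section 4.2.2.1 bars concomitant treatment by default and introduces the appendix only as an addition, with onward referral to the Investigator's Brochure or sponsor. Exclusion 7 has its own catch-all, and the stopping rule also cites section 4.2.2 and so reaches the general bar. The two statements in 1.4.2 can be read as a binding rule for this trial, which the appendix matches, followed by programme-level advice.

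Much of this stands, and it is why the point is small. It does not remove the mismatch. The default bar gives way exactly when an adverse event needs treatment, and that is when the list is consulted. Reading the second statement as advice still leaves its transporter sentence pointing to a list that omits seven of the eight transporters.

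A reader might infer more than the documents support:

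- **That the omitted medicines need a washout before randomisation.** The second statement in 1.4.2 is about giving medicines together. No BI 730357 is present before Day 1, and the documents do not quantify carry-over of an earlier medicine. Use in the preceding week is a weak route.
- **That exposure has no room to rise.** The 400 mg QD steady-state AUC of 35,500 is 35,500 / 35,200 = 1.01 times the rat AUC in 1.4.2. But that rat level is one at which no cutaneous reaction was seen, and Cmax is 2,210 / 4,520 = 0.49 of the rat value. The 300 mg BID group deliberately goes to 600 / 400 = 1.5 times the daily dose. With no effect size for weaker inhibitors, these ratios do not measure the gap.
- **That 10 of 13 describes a large set of medicines.** It counts enzyme and transporter labels. The qualifiers in 1.4.2 (patient risk, sensitivity, narrow window) would leave few candidates among healthy volunteers.
- **That the photosensitivity comparison is compromised.** Nothing in the documents shows this, and the primary and secondary assessments all fall during residence.

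**Conclusion.** The point holds as a minor safety inconsistency. The difference between the texts is certain: CYP3A inhibitors weaker than moderate, and 10 of the 13 substrate classes, are in the advice but not in the list, and 4.2.2.2 repeats the narrower scope for foods. The practical consequence is small: mainly AE therapy at investigator judgment in BI 730357 recipients and, to a lesser degree, medicines taken after discharge while drug may remain. The food part is marginal, because subjects eat the site diet through all dosing and all on-treatment skin assessments.

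This rests on two judgments the documents do not quantify: that few healthy volunteers would be given an omitted medicine, and that investigators would usually apply the default bar or ask the sponsor. No endpoint, sample-size figure or planned analysis changes.

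**What to change.** 1. In Appendix 10.1, extend the CYP3A row to all known CYP3A inhibitors and keep the strong-or-moderate limit for inducers. Make the same change to the food wording in 4.2.2.2.
2. Add to Appendix 10.1, with the qualifiers used in 1.4.2, the CYP2C8, 2C9 and 2C19 substrates and the BCRP, OATP1B1, OATP1B3, OAT3, OCT2, MATE1 and MATE2-K substrates. Restrict them from first dose to EOT, or use the existing window for simplicity.
3. Keep the P-gp, CYP1A2 and CYP2B6 entries as they are.
4. In 1.4.2, merge the two CYP3A sentences into one that keeps the force of a prohibition and applies it to all known CYP3A inhibitors and to strong or moderate inducers. Deleting the first sentence outright would be a mistake, because it is the only CYP3A text there that prohibits and does not merely advise.

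The cost is a few lines in an amendment and a slightly narrower choice of symptomatic therapy.

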1.4.3 Discussion

The nature of the target and the mechanism of action of BI 730357 as well as of Ciprofloxacin are well understood.

In the context of the unmet medical need and anticipated benefit of BI 730357, the benefitrisk evaluation of the compounds, based upon preclinical and clinical information available to date, is considered favourable and healthy subjects in this trial will not be exposed to undue

BI Trial No.: 1407-0037

c27983101-03 Clinical Trial Protocol Page 27 of 79

Proprietary confidential information © 2020 Boehringer Ingelheim International GmbH or one or more of its affiliated companies

safety risks in relation to the important information expected from this trial as a basis for further clinical development of BI 730357.

Considering the medical need of the development of a better tolerated and more effective oral treatment for patients with PsO and other Th17-mediated diseases, the Sponsor considers that the benefit outweighs the potential risks and justifies exposure of healthy human volunteers.

c27983101-03 Clinical Trial Protocol Page 28 of 79

Proprietary confidential information © 2020 Boehringer Ingelheim International GmbH or one or more of its affiliated companies

